5.6 Descriptive Statistics

All continuous variables will be summarized by presenting the number of subjects, mean, standard deviation (SD), median, Q1, Q3, minimum, and maximum. For PK endpoints, geometric statistics including geometric mean and coefficient of variation (CV) will also be provided.

Categorical variables will be presented as frequencies and percentages.

Summary tables will be presented by visit, when applicable.

Change from baseline will be calculated as:

Assessment value at postbaseline visit X – baseline value.

Percent change from baseline will be calculated as:

(Assessment value at postbaseline visit X – baseline value) \times 100% / (baseline value)

Percent change from baseline will be missing in situation where baseline value equals to 0.

5.7 Statistical Tests

Unless otherwise specified, all statistical tests will be two-sided and will be performed with a significant level of 0.05. Confidence intervals (CIs) will be two-sided with 95% coverage.

5.8 Handling of Retests, Unscheduled Visits, and Early Termination Data

Retests measurements, Unscheduled measurements, and ET visit assessments will be included in analysis and be summarized via analysis visit windowing according to the windowing conventions in section 5.4.

All data from retest, unscheduled measurements and ET visit assessments will be listed.

5.9 Software Version

All analyses will be performed using SAS® software Version 9.4 or higher.

	STATISTICAL ANALYSIS PLAN, Version 1.0
Protocol Number: ARQ-151-312	Sponsor: Arcutis Biotherapeutics, Inc.

6 STATISTICAL CONSIDERATIONS

6.1 Adjustments for Covariates

Covariates for this study include pooled study site and baseline vIGA-AD (vIGA-AD=2 - Mild vs. vIGA-AD=3 - Moderate at randomization). Subgroup analyses will be generated for the baseline covariates.

6.2 Handling of Dropouts or Missing data

See Appendix 2 for handling of completely or partially missing dates for prior and concomitant medications and AEs.

Unless otherwise specified, missing safety data will not be imputed.

6.2.1 Multiple Imputation

For the primary efficacy endpoint of vIGA-AD success at Week 4 and the secondary endpoint of vIGA-AD success at Week 4 among subjects with a 'Moderate' randomized vIGA-AD score, the primary analysis will impute missing values using a Predictive Mean Matching (PMM) sequential-regression multiple imputation model for the ITT population. This is a three-step process.

1. The first step is to understand the pattern of missingness. In order to perform the multiple imputation, a monotone missing pattern has to be achieved. For example, if there exist values for baseline and Week 4 visits, but missing values for the Week 1 or 2 visits, the Markov-Chain Monte-Carlo (MCMC) method will be used to impute the small amount of missing data that may be missing at the intermediate visits that is required to make the missing data pattern monotone before applying the multiple imputation algorithm. This method uses a non-informative Jeffreys prior to derive the posterior mode from the expectation-maximization (EM) algorithm as the starting values for the MCMC method. The MCMC method will use the seed 6457149. The vIGA-AD score will be treated as a continuous variable for this step and the model will include the vIGA-AD scores at baseline, Week 1, Week 2, and Week 4. To avoid values that could not be observed in practice, imputed values will be rounded to the nearest integer (Round=1 option in PROC MI) in the range of 0 to 4.

To determine the number of multiply-imputed datasets to be created at this step, the proportion of datapoints with non-monotone pattern across all visits and subjects will first be derived as follows:

	STATISTICAL ANALYSIS PLAN, Version 1.0
Protocol Number: ARQ-151-312	Sponsor: Arcutis Biotherapeutics, Inc.

 $\frac{number\ of\ non\ monotone\ visits\ accross\ all\ visits\ and\ subjects}{total\ number\ of\ expected\ visits\ across\ all\ subjects}*100$

Then, the following table will be used:

Non-monotone	Number of
Missing Data	Imputed Datasets
≤ 2%	1
$> 2\%$ to $\le 5\%$	3
> 5%	10

- 2. Once the monotone pattern is achieved, the next step is to implement the imputation algorithm. For this, the PMM regression method will be used. This method is particularly helpful if the normality assumption is violated. For subjects with complete data up to a particular visit, a PMM regression model will be fit that includes the outcome at that visit as the dependent variable and as independent variables, the treatment group, pooled study site, and vIGA-AD score outcomes at previous visits, using a seed of 482371. For other scales/questionnaires, the actual baseline vIGA score will also be included as an independent variable. This process will be repeated 25 times, resulting in a total of 25 to 250 complete analysis datasets, depending on the number of imputed monotone datasets that are required. The seed may be changed after unblinding in case of any issues with the imputation process, and it will be documented in the CSR if any change is required.
- 3. For each completed dataset, compute the necessary derived variables. The dichotomous success rate (clear or almost clear with at least a 2-point change from baseline) will be derived. For each of the 25 to 250 complete analysis datasets, the results will be analyzed using a CMH analysis, adjusted for the pooled study site and randomized vIGA-AD score for the primary efficacy endpoint and adjusted for the pooled site for the secondary efficacy endpoint. Results will be combined into one multiple imputation inference as follows:
 - a. Common proportion of success, common Mantel-Haenszel (MH) proportion difference (and associated 95% CI), and common MH odds ratio (and associated common 95% CI) will be combined using PROC MIANALYZE based on Rubin's rule. Common MH odds ratios and associated common 95% CI will first be normalized using a log-transformation before being combined using PROC MIANALYZE. The resulting combined common MH odds ratio and associated combined common 95% CI will be back-transformed to the arithmetic scale before being presented in a table.

	STATISTICAL ANALYSIS PLAN, Version 1.0
Protocol Number: ARQ-151-312	Sponsor: Arcutis Biotherapeutics, Inc.

- b. For the combined common proportion of success, the associated combined common 95% CI will be calculated as per Lott and Reiter multiple imputation Wilson interval method¹.
- c. Two p-values will be produced for each analysis:
 - i. The primary p-value will be obtained from a multiple imputation CMH test, where CMH general association statistics and their standard errors obtained from the analysis of each multiply-imputed dataset will be transformed as per Wilson-Hilferty² before being combined using PROC MIANALYZE based on Rubin's rule. Because the Wilson-Hilferty transformation is a monotone transformation, the p-value for the CMH test is the one-sided p-value from the t distribution. This p-value will be the primary p-value used to evaluate the result according to the multiple testing strategy described in Section 6.5.
 - i. Should the common MH odds ratio from the analysis of at least one of the multiply-imputed datasets be not estimable, combined common MH odds ratio and associated combined common 95% CI and p-value will not be presented. Under such circumstance, conclusions will be based on the p-value obtained from a multiple imputation test of the proportion difference, where the common proportion difference using MH weights and associated common standard errors based on the Sato variance estimator obtained from the analysis of each multiply-imputed dataset will be combined using PROC MIANALYZE based on Rubin's rule.

Similar multiple imputation method will be used for the average weekly WI-NRS and EASI total score.

For the average weekly WI-NRS, it's the missing average weekly WI-NRS data (i.e., those that cannot be computed because only 3 or less non-missing assessments are available during a given week) at Weeks 1, 2, 3, and 4 that will be multiply imputed, not the missing daily WI-NRS data. Since the missing average weekly WI-NRS values have a precision of 1 decimal place, the MCMC imputation for the non-monotone missing data will be restricted to values between 0 and 10, rounded to the 1st decimal (i.e., 0.1). Imputation of missing data for WI-NRS will be based on the ITT population, i.e., all randomized subjects will be included in the imputation process.

For the EASI total score, it's the missing EASI total score data at Weeks 1, 2, and 4 that will be imputed, not the missing EASI question score data. Since the missing EASI total scores have a precision of 1 decimal place, the MCMC imputation for the non-monotone missing data will be

	STATISTICAL ANALYSIS PLAN, Version 1.0
Protocol Number: ARQ-151-312	Sponsor: Arcutis Biotherapeutics, Inc.

restricted to values between 0 and 72, rounded to the 1st decimal (i.e., 0.1). Imputation of missing data for EASI total score will be based on the ITT population.

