6.5 Multiple Comparisons/Multiplicity

To control for familywise type I error at level of 0.05, the secondary endpoint of vIGA-AD Success at Week 4 for subjects with vIGA-AD score of 'Moderate' at randomization will only be tested if the primary endpoint demonstrates statistical significance. In addition, the remaining secondary endpoints will be inferentially tested only if the primary and the secondary endpoint (vIGA-AD Success at Week 4 for subjects with vIGA-AD score of 'Moderate' at randomization) comparisons are statistically significant using hierarchical testing procedure by partitioning of alpha.

Upon successful demonstration of statistical significance for the primary and above secondary endpoint, the remaining endpoints will be grouped into secondary endpoint family 1, comprised of the 4-point reduction on the WI-NRS at Week 4, Week 2 and Week 1, and secondary endpoint family 2, comprised of the EASI-75 at Week 4, vIGA-AD of 'clear' or 'almost clear' at Week 4,

	STATISTICAL ANALYSIS PLAN, Version 1.0
Protocol Number: ARQ-151-312	Sponsor: Arcutis Biotherapeutics, Inc.

vIGA-AD of success at Week 2 and Week 1, vIGA-AD of 'clear' or 'almost clear' at Week 2 and Week 1. An alpha level of 0.03 will be used to test the endpoints in the secondary endpoint family 1 sequentially. An alpha level of 0.02 will be used to test the endpoints in secondary endpoint family 2 sequentially.

In addition to the partitioning of the overall 0.05 alpha into two families, the Fallback Method will be applied. The fallback method is a modification of the fixed-sequence method, providing opportunity to test an endpoint later in the sequence even if an endpoint tested early in the sequence has failed to show statistical significance. The order of the endpoints remains important. The appeal of the fallback method is that if an endpoint later in the sequence has a robust treatment effect while the preceding endpoint is unsuccessful, there is a modest amount of alpha retained as a fallback to allow interpretation of that endpoint without inflating the Type I error rate. Applying the fallback method begins by dividing the total alpha (not necessarily equally) among the endpoints and maintains a fixed sequence for the testing. In this study, the Fallback Method will be applied to the fixed sequence of testing Family 1, and then Family 2.

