As the testing sequence progresses, a successful test preserves its assigned alpha as "saved" ("unused" or "accumulated") alpha that is passed along to the next test in the sequence, as is the case for the sequential method. This accumulated alpha is added to the prospectively assigned alpha (if any) of that next endpoint and the summed alpha is used for testing that endpoint. Thus, as sequential tests are successful, the alpha accumulates for the endpoints later in the sequence; these endpoints are then tested with progressively larger alphas.

[figure not shown]
In this study, the Fallback Method will be applied following this sequence:

Family 1: Testing will proceed at the 0.03 level sequentially within Family 1. Should all 3 endpoints in Family 1 be statistically significant at the 0.03 level, then the full 0.03 alpha will be carried to Family 2. Family 2 would then be tested at the full (α =0.02+0.03=0.05).

Should, anywhere during the sequential testing of Family 1, there is a p-value >0.03, the testing within Family 1 will stop, and no additional alpha can be carried over to Family 2.

	STATISTICAL ANALYSIS PLAN, Version 1.0
Protocol Number: ARQ-151-312	Sponsor: Arcutis Biotherapeutics, Inc.

Figure 2 Multiple Testing Scheme

Achievement of vIGA-AD success is a score of "clear" or "almost clear" plus a 2-grade improvement from baseline.

WI-WRS Success is a 4-point reduction in WI-NRS among subjects ≥12 years old with WI-NRS ≥ 4 at baseline.

EASI-75: achievement of at least a 75% reduction in the Eczema Area and Severity Index

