12.2 Secondary Endpoints Analysis

Secondary efficacy endpoints are based on the vIGA-AD scale, WI-NRS scale or EASI questionnaire. The list of secondary efficacy endpoints can be found in Section 2 and their derivation in Section 5.5.

• For more details about the vIGA-AD scale refers to Section 12.1.1.

	STATISTICAL ANALYSIS PLAN, Version 1.0
Protocol Number: ARQ-151-312	Sponsor: Arcutis Biotherapeutics, Inc.

- The WI-NRS scale is a single item scale assessing the subject-reported worst itch severity during the previous 24-hour period. The scale is from 0 to 10 ('no itch' to 'worst itch imaginable').
- For the EASI questionnaire, four anatomic sites (head, upper extremities, trunk, and lower extremities) are assessed for erythema, induration/infiltration (papules), excoriation, and lichenification as seen on the day of the examination. The severity of each sign is assessed using a 4-point scale (half steps are allowed e.g., 0.5): 0 (none), 1 (mild), 2 (moderate), and 3 (severe). The area affected by AD within a given anatomic site is estimated as a percentage of the total area of that anatomic site and assigned a numerical value according to the degree of AD involvement as follows: 0 (no involvement), 1 (1-9%), 2 (10-29%), 3 (30-49%), 4 (50-69%), 5 (70-89%), and 6 (90-100%).

For each secondary efficacy endpoint, missing data will be imputed and data will be summarized as for the primary efficacy endpoint (refer to Section 12.1.3).

Upon successful demonstration of statistical significance for the primary efficacy endpoint, the secondary efficacy endpoint of vIGA-AD success among subjects with vIGA-AD score of 'Moderate' at randomization will be analyzed as described for the primary efficacy endpoint (refer to Section 12.1.3) but based on the vIGA-AD Moderate ITT population (refer to Section 4.4) and stratifying by pooled study site only. That is, as per the vIGA-AD Moderate ITT population definition all subjects included in this analysis will have a randomized vIGA-AD score of Moderate (3) and so, the CMH test cannot be stratified by randomized vIGA-AD score.

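### The first imputation step (MCMC) leaves treatment out, so intermittently missing Week 1 and Week 2 values are filled from a model that pools the two arms

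*SAP*

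**What the plan says.** SAP section 6.2.1 describes a three-step process. Step 1 uses MCMC to fill what the SAP calls the "small amount of missing data that may be missing at the intermediate visits", so that the missing-data pattern becomes monotone. For this step it states that "the model will include the vIGA-AD scores at baseline, Week 1, Week 2, and Week 4". It mentions neither treatment, nor site, nor a run by arm. Step 2 is predictive mean matching, and there the predictors are spelled out: "the treatment group, pooled study site, and vIGA-AD score outcomes at previous visits".

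For the other scales, section 6.2.1 says: "Similar multiple imputation method will be used for the average weekly WI-NRS and EASI total score". It gives ranges and rounding for their MCMC step but no variable list.

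The scheme reaches beyond Week 4. Section 12.2 says: "For each secondary efficacy endpoint, missing data will be imputed and data will be summarized as for the primary efficacy endpoint". The secondary endpoints include WI-NRS response at Weeks 4, 2 and 1 (Family 1) and, as the last four tests of Family 2, vIGA-AD success and clear/almost clear at Weeks 2 and 1. On Family 1, section 6.5 says: "An alpha level of 0.03 will be used to test the endpoints in the secondary endpoint family 1 sequentially". The transfer of that alpha to Family 2 has a condition: "Should all 3 endpoints in Family 1 be statistically significant at the 0.03 level".

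**The concern.** An imputation model should contain the contrast that will be tested on the completed data. Step 2 meets this and step 1, as written, does not. Step 2 cannot repair the omission, because a value filled at step 1 is treated as observed from then on. The SAP's own example, a subject with baseline and Week 4 scores but no Week 1 or Week 2 score, is exactly this case.

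Six alpha-controlled tests use such values: WI-NRS at Weeks 2 and 1, and vIGA-AD success and clear/almost clear at Weeks 2 and 1. Both WI-NRS tests also help decide whether 0.03 passes to Family 2. Week 4 is the last visit, so a missing Week 4 value is always filled at step 2 with treatment in the model. The primary endpoint, the Moderate secondary and EASI-75 are touched only through a filled earlier score used as a predictor.

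A lesser point concerns the number of step 1 draws. When non-monotone data are 2% or less, one step 1 dataset is reused in all 25 completed datasets, so its uncertainty adds nothing to Rubin's between-imputation variance.

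**Working it through.** **Plan's own figure.** Step 1 yields 1, 3 or 10 datasets and step 2 repeats 25 times: 1 × 25 = 25, 3 × 25 = 75, 10 × 25 = 250. This reproduces the stated range of 25 to 250.

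**Mechanism.** Take Week 1 missing with Weeks 2 and 4 observed, and baseline balanced. Under a pooled model the arm difference among imputed values is b2·Δ2 + b4·Δ4, where Δ is the effect at a visit and b its regression weight. It should be Δ1. The bias in the risk difference is

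share missing × (imputed difference without treatment − imputed difference by arm).

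It is negative when the early effect exceeds what later visits predict, and positive when onset is late.

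**Inputs.** From the SAP: 650 subjects, 2:1 allocation, Week 4 success 37% vs 22%, family alphas 0.03 and 0.02. Assumed: 2%, 5% or 10% intermittently missing per visit (2% and 5% are the SAP's cut-points for the number of step 1 datasets), 75% Moderate, the Week 1 and 2 effects, and the visit correlations.

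**Large-sample check** (600,000 subjects; integer scores 0–4; latent adjacent-visit correlation 0.4 or 0.7).

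- Constant effect, correlation 0.4, Week 1 success: true difference 10.6 points. Imputed values show 5.1 without treatment, 10.5 with treatment as covariate, 10.6 by arm. Bias at 5% missing: 0.05 × (5.1 − 10.6) = −0.28 points.
- Late effect, correlation 0.7, Week 1 clear/almost clear: true difference −0.2. Imputed values show 3.2 without treatment and 0.0 by arm. Bias at 5%: 0.05 × 3.2 = +0.16 points.

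Range of bias over success and clear/almost clear at Weeks 1 and 2, in percentage points:

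| Effect over time | 2% missing | 5% missing | 10% missing |
|---|---|---|---|
| Early, fading | −0.07 to −0.21 | −0.17 to −0.53 | −0.34 to −1.06 |
| Constant | −0.04 to −0.14 | −0.09 to −0.34 | −0.19 to −0.68 |
| Late | +0.01 to +0.06 | +0.03 to +0.16 | +0.06 to +0.31 |

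With treatment in step 1, as covariate or by arm, the difference among imputed values was within 0.8 points of the truth in every scenario.

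**Trial-size check, vIGA-AD success** (4,000 trials of 650 per cell; visit correlations 0.55–0.70; Week 1/2 values deleted at random with Week 4 kept). Vehicle success was 5/12/22% at Weeks 1/2/4. Active was 11.5/23/37% (early), 8/18/37% (gradual) or 5/12/37% (late). The same trials were imputed with and without treatment.

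| Effect of omitting treatment | 2% | 5% | 10% |
|---|---|---|---|
| Early, Week 1 bias (true 6.5 points) | −0.04 | −0.10 | −0.21 |
| Early, Week 2 bias (true 11.0 points) | −0.04 | −0.09 | −0.19 |
| Late, Week 2 bias (true 0) | +0.06 | +0.16 | +0.34 |
| Early, Week 1 power change at alpha 0.02, points | −0.9 | −1.4 | −4.0 |
| Early, Week 2 power change at alpha 0.02, points | −0.2 | −0.4 | −0.7 |

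Gradual onset gave bias within 0.06 and power changes within 1.2 points, either way. Simulation error on the early Week 1 power changes is 0.2–0.4 points. With treatment in step 1 the bias was 0.03 or less in every cell. With late onset, rejection was 1.5–2.2% at the 2% level, with or without treatment.

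**Trial-size check, WI-NRS** (3,000 trials per cell; imputed on 650, about 300 tested; adjacent-week correlation 0.85; alpha 0.03). Early onset, Week 1: bias −0.04, −0.09 and −0.18 points (true 9.3); power change 0.0, −0.8 and −1.4 points. Late onset, Week 2: bias up to +0.19; rejection 2.3–3.1%.

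**Step 1 draws.** With m draws each copied 25 times, the step 1 variance counted is (25m/(25m−1))·((m−1)/m)·(1+1/(25m))·B, against (1+1/m)·B needed.

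- m = 1: 0 against 2B, so 0% is counted.
- m = 3: 0.685B against 1.333B, so 51%.
- m = 10: 0.907B against 1.1B, so 82%.

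B/W was 0.019, 0.048 and 0.095 at 2%, 5% and 10% missing (early-onset Week 1 cells). The standard error ratios are √(1/1.038) = 0.982, √(1.033/1.064) = 0.985 and √(1.086/1.1045) = 0.992. The standard error is understated by about 1.8%, 1.5% and 0.8%.

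**The case against.** The case for leaving the text alone is one of materiality. The primary, the Moderate secondary and EASI-75 do not depend on this step. The SAP itself expects few intermediate gaps. The contiguous visit windows in section 5.4 (days 2–11 for Week 1, 12–22 for Week 2) let unscheduled and early-termination assessments stand in for a missed visit, so 10% intermittent missingness is a stress case for vIGA-AD. Section 12.2 plans non-responder and observed-data analyses for all six tests where the hierarchy allows, and neither uses step 1. If Family 1 passes, Family 2 is tested at 0.05 and the loss shrinks: in a rerun at a lower correlation setting, the early-onset Week 1 loss was 0.3, 1.0 and 2.1 points at 0.05, against 0.5, 2.0 and 3.3 at 0.02. These are stand-alone powers for tests late in a fixed sequence.

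All of this bears on size, and it stands as such. None of it corrects the imputation that produces the primary p-value for those tests. Four limits also stand:

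- The SAP does not forbid a by-arm run in code; pooled arms is the plain reading.
- The WI-NRS omission is inferred, because no step 1 variables are listed. Weekly diary averages may well have more gaps, since a week with three or fewer entries counts as missing.
- The type I error check used 10 proper draws throughout, not the SAP's 1 or 3 at the lower missingness levels.
- The simulations pooled a severity-stratified risk difference, not the transformed CMH statistic that the SAP will use.

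**Conclusion.** The concern holds, as a minor point. As written, step 1 gives slightly biased Week 1 and Week 2 imputations. At 5% intermittent missingness the bias in the risk difference ranged from −0.53 points (early, fading effect) to +0.16 (late effect). At 10% it ranged from −1.06 to +0.34. Under early onset, the simulated Week 1 vIGA-AD power loss at alpha 0.02 was 0.9 to 4.0 points across 2–10% missing. The missingness rates, early effects and correlations are assumptions, so the range matters more than any single figure. Neither a change in a Week 4 conclusion nor type I error inflation was found, within the limits given above. The case for acting is that the bias is avoidable at almost no cost.

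**What to change.** In SAP section 6.2.1, step 1, state that the MCMC model includes the treatment indicator or that it is run separately by treatment group. Apply this to vIGA-AD and weekly WI-NRS, and to EASI for consistency only, since EASI-75 is tested only at Week 4. List the step 1 variables for WI-NRS explicitly.

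Optionally, take 25 step 1 draws with one predictive mean matching imputation each, so that step 1 uncertainty is counted in Rubin's variance even when non-monotone data are 2% or less.

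The main change costs one SAP sentence and one SAS statement. It needs no new data and leaves sample size, alpha and the 25–250 dataset count as they are. The optional change would fix the count at 25.

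### Intermittent Week 1 and Week 2 gaps are drawn only 1, 3 or 10 times but pooled as 25, 75 or 250 independent imputations, so their variance is under-counted and secondary p-values depend needlessly on the seed

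*SAP*

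**What the plan says.** SAP 6.2.1 imputes in two stages.

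- **Step 1** makes the missing pattern monotone by MCMC. For vIGA-AD, "the model will include the vIGA-AD scores at baseline, Week 1, Week 2, and Week 4"; treatment and site are not in it. A table introduced by "To determine the number of multiply-imputed datasets to be created at this step" sets the number of copies: 1 at 2% non-monotone data or less, 3 above 2% up to 5%, 10 above 5%.
- **Step 2** runs PMM on each monotone copy: "This process will be repeated 25 times, resulting in a total of 25 to 250 complete analysis datasets".
- **Step 3** analyses every dataset. Estimates "will be combined using PROC MIANALYZE based on Rubin's rule". The CMH statistics behind the primary p-value "will be transformed as per Wilson-Hilferty² before being combined using PROC MIANALYZE based on Rubin's rule". No nested combining rule is mentioned.

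The scheme is not confined to the primary endpoint. SAP 6.2.1 adds: "Similar multiple imputation method will be used for the average weekly WI-NRS and EASI total score". SAP 12.2 states: "For each secondary efficacy endpoint, missing data will be imputed and data will be summarized as for the primary efficacy endpoint". On multiplicity, SAP 6.5 says: "An alpha level of 0.03 will be used to test the endpoints in the secondary endpoint family 1 sequentially". The 0.03 moves on to Family 2 only if all three WI-NRS tests succeed.

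**The concern.** Rubin's rule is valid when each completed dataset is an independent draw of all the missing values. Here a Week 1 or Week 2 score that is missing before a later observed visit is filled in step 1 and not touched again. In the lowest tier it is the same number in all 25 datasets, so it contributes no between-imputation variance at all. In the other tiers the datasets form 3 or 10 clusters of 25 but are pooled as 75 or 250 separate draws.

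Six alpha-controlled tests use Week 1 or Week 2 outcomes: WI-NRS 4-point reduction, vIGA-AD Success, and vIGA-AD clear or almost clear, each at both weeks. The two WI-NRS tests also act as gates. They help decide whether Family 2, which begins with EASI-75 at Week 4, is tested at 0.05 or 0.02. At stake are the stated precision of these tests and how far a result near its threshold depends on a random seed.

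**Working it through.** **1. The plan's own count.** Copies M times PMM repeats N = 25 gives 1 × 25 = 25, 3 × 25 = 75 and 10 × 25 = 250. This reproduces the stated 25 to 250.

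**2. How many gaps the lowest tier allows.** With 650 subjects and three post-baseline vIGA-AD visits there are 1,950 visits, and 2% of these is 39. Split evenly over Weeks 1 and 2, that is 19.5/650 = 3% of subjects per visit. If all fall at one visit, it is 39/650 = 6%.

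**3. Variance counted against variance needed.** Let U be the complete-data variance, B the variance between step 1 copies and W the variance between PMM draws within a copy.

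- Needed: U + (1 + 1/M)B + (1 + 1/(MN))W.
- Expected from single-level Rubin: U + (1 + 1/(MN))(W + fB), with f = N(M−1)/(MN−1).

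| M | f | B counted: f(1 + 1/(MN)) | B needed: 1 + 1/M |
|---|---|---|---|
| 1 | 0 | 0 | 2.0 |
| 3 | 50/74 = 0.676 | 0.685 | 1.33 |
| 10 | 225/249 = 0.904 | 0.907 | 1.1 |

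This step is algebra and needs no assumption about the amount of missing data.

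**4. Size of the effect.** The documents give no missing-data rate, so the following is assumed: 13 to 150 gaps among 1,950 visits, 6% dropout, and Week 2 vIGA-AD Success of about 18 to 22% on active and 11 to 15% on vehicle. The simulation used N = 650 at 2:1, 26 pooled sites by 2 severity strata, MCMC with rounding, PMM, and the Wilson-Hilferty pooled CMH test. There is one illustrative dataset per row.

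| Gaps | M | U | W | B | SE reported/needed |
|---|---|---|---|---|---|
| 13 (0.7%), split | 1 | 0.07384 | 0.001995 | 0.000952 | 0.988 |
| 39 (2%), split | 1 | 0.05386 | 0.001309 | 0.001017 | 0.982 |
| 39 (2%), all Week 2 | 1 | 0.05325 | 0.001373 | 0.001852 | 0.968 |
| 97 (5%), split | 3 | 0.06260 | 0.001900 | 0.006030 | 0.973 |
| 150 (7.7%), split | 10 | 0.06367 | 0.002117 | 0.006316 | 0.992 |

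Worked example, third row: reported 0.05325 + 1.04 × 0.001373 = 0.05468; needed 0.05468 + 2 × 0.001852 = 0.05838; √(0.05468/0.05838) = 0.968.

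**5. Dependence on the seed.** The table gives the 5th to 95th percentile of the Week 2 p-value over seeds, with the data held fixed.

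| Gaps | As planned | 25 copies × 1 PMM | 100 copies × 1 PMM |
|---|---|---|---|
| 13, split | 0.003–0.008 | 0.004–0.006 | 0.004–0.005 |
| 39, split | 0.003–0.010 | 0.005–0.008 | 0.006–0.007 |
| 39, all Week 2 | 0.013–0.055 | 0.023–0.034 | 0.025–0.030 |
| 97, split | 0.009–0.037 | 0.016–0.029 | 0.019–0.024 |
| 150, split | 0.068–0.129 | 0.075–0.121 | 0.088–0.105 |

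In the third row the median p-value with 100 copies is 0.028, yet 35% of seeds under the planned scheme give 0.02 or less. In the one-copy rows the seed-to-seed SD of the Week 2 log odds ratio is 0.11 to 0.19 of its standard error.

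**The case against.** The strongest reply is that no harm to the error rate has been shown. A reader might turn the SE deficits into inflated levels: about 0.021 to 0.024 for a nominal 0.02 test and 0.031 to 0.036 for a nominal 0.03 test. That conversion ignores the step 1 model. Because treatment is left out of it, the filled values are shrunk towards no difference, which offsets the missing variance. In simulated null trials of Week 1 Success with one draw and that model, the error was 4.6 to 5.4% at nominal 5%. With 2,500 to 4,000 trials the Monte Carlo margin is about ±0.7 to 0.85 points, so this cannot be told apart from 5%. Inflation (5.8% at nominal 5%, 2.5% at nominal 2%) appeared only with treatment added to step 1, which the SAP does not specify. This objection stands, although it means that one weakness happens to mask another.

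Other points also stand:

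- Literal single-draw noise belongs to the lowest tier only. At 10 copies the SE deficit is 0.8%.
- If the whole 2% allowance falls at one visit, the other visit has no intermittent gaps. The worst case therefore cannot apply to all six tests at once.
- WI-NRS was not simulated. It has four imputed weeks, is imputed over the full ITT population, and is tested in a subset.
- The plan limits the gaps. The SAP 5.4 windows are contiguous and can take in unscheduled or early termination visits, and SAP 5.5 needs only 4 of 7 diary days.
- SAP 12.2 adds non-responder and observed-data analyses for these endpoints. They do not use the MCMC draw and could expose a fragile result, but they do not repair the pooled p-value that decides the test.

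The fixed seeds in SAP 6.2.1 make the result reproducible but not less dependent on the draw. The SAP does allow a seed change after unblinding if imputation runs into problems. That sentence sits in the PMM step, so it should not be read as clearly covering the MCMC seed.

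**Conclusion.** The combining rule does not fit the imputation scheme. For intermittent Week 1 and Week 2 gaps it counts 0, 0.69 or 0.91 of B where 2.0, 1.33 or 1.1 is needed. In the lowest tier the estimate rests on one random draw of those values. The consequence is modest: Week 2 standard errors about 1 to 3% too small (0.8 to 3.2% in the assumed scenarios), and seed dependence that matters only when a p-value lies near its threshold. These sizes rest on an assumed missing-data rate and one illustrative dataset per scenario. The size for WI-NRS is unknown.

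Two stronger readings are not supported. The documents and calculations do not show an inflated type I error for the plan as written. Nor do they put the primary result in doubt: a subject with an intermittent gap normally has Week 4 observed, and otherwise the filled score serves only as a predictor. The same holds for the Moderate endpoint. The only route to Week 4 tests is indirect, through the Family 1 gate. The change is still worth making, because it restores a valid variance and removes avoidable noise at very little cost.

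**What to change.** In SAP 6.2.1, delete the 1/3/10 table. Create M independent monotone MCMC datasets, with M fixed in advance, draw one PMM imputation from each, and pool the M results by ordinary Rubin's rules. Choose M so that draws for subjects who drop out before Week 4 are not reduced: 25 × 1 would be valid, but would cut them from 75 or 250 to 25 in the upper tiers. An M of 100 to 250 largely or fully avoids that. State that the same M applies to vIGA-AD, WI-NRS and EASI.

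Alternatively, keep the nested scheme with at least 2 MCMC copies in every tier and specify nested (two-stage) combining rules. This corrects the variance but leaves more seed noise when copies are few.

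The cost is a short SAP edit, changed imputation counts in two program steps and slightly more computation. The alternative also needs code for the nested rule. No new data are needed. The edit should be made before unblinding.
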